10.1 Variables and derivations

The trial classifications are defined as follows:

Screening failure:

Individuals who do not meet the criteria for participation in this study (screen failure) at the initial visit may be later rescreened only once. The interval between screening and rescreening should be at least 4 weeks.

Completed treatment:

All the subject who have taken all the treatment as per protocol.

Completed trial:

Participants who completed the trial, as indicated on the [End of Study] page of the (eCRF), will be assumed to have completed trial.

Lost to follow-up:

A subject will be considered lost to follow-up if he or she repeatedly fails to return for scheduled visits and is unable to be contacted by the study site. Site personnel are expected to make diligent attempts to contact subjects who fail to return for a scheduled visit or were otherwise unable to be followed up by the site.

Early withdrew from trial:

Participants who discontinued from the trial, as indicated on the [End of Study] page of the (eCRF), will be assumed to have withdrew early from trial.

The following parameters will be summarised for the subject's disposition table as per eCRF:

- Number of screening failure subjects (This will be applicable for ENRL set table only.)
- Number of subject's completed trial
- Number of subject's completed treatment
- Number of subjects withdrew early from trial

- Number of Subject's in ENRL set
- Number of Subject's in FAS set
- Number of Subject's in PP set

The following parameters will be summarised for the early withdrawals table as per eCRF Subject's primary reason for discontinuation (reasons mentioned in eCRF "End of the Study" form) which is as follows:

- ADVERSE EVENT
- DEATH
- SCREEN FAILURE
- WITHDRAWAL BY SUBJECT
- PHYSICIAN DECISION
- NON-COMPLIANCE WITH STUDY DRUG
- PROTOCOL DEVIATION
- STUDY TERMINATED BY IRB OR ERB
- STUDY TERMINATED BY SPONSOR
- LOST TO FOLLOW-UP
- LACK OF EFFICACY
- OTHER

Derivations:

- In eCRF at End of the study form primary reason for discontinuation is indicated as "SCREEN FAILURE" to ensure that subject is screen failure.
- In eCRF at End of Study form Subject status is indicated as "COMPLETED" to ensure that subject is completed trail.
- If the date of last dose of study treatment < Date of Visit (Visit 8(Week 24)) and date of last dose of study treatment > Date of Visit (visit 7(week 20)) to ensure that subjects is completed treatment.

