16.1 Variables and derivations

Adverse Events (AEs) will be coded using MedDRA central coding dictionary, Version (refer to DMP for dictionary version).

Adverse events (AE) and Serious adverse event (SAE) are defined as events that are reported after the signing the inform consent form (ICF).

Treatment-emergent adverse events (TEAEs) are defined as events that are newly reported after the first study drug treatment or are reported to have worsened in severity after the first study drug treatment. In the case where it is impossible to define an AE as treatment-emergent or not, the AE will be classified by the worst case assigned, i.e. a TEAE.

In section 24 Appendix 2 the algorithm is given for calculation of partial date imputation for adverse events (AEs) and it will be used for partially missing adverse event start and end date imputation.

Each adverse event will be described by following in listing:

- Subject Number
- Description (AE term) i.e. System organ class/ Preferred terms / Reported terms
- Duration (start and end dates)
- Severity of event
- Relationship to the investigational product
- Relationship to non-study drug treatment
- Relationship to the study procedure
- Action taken with the study treatment
- Outcome
- Whether SAE or not

Each serious adverse event will be described by following in listing:

Subject Number

CONFIDENTIAL CS.BS.01.00 TPL-1.0: Statistical Analysis Plan Template Page 41 of 85

- Description (SAE term) i.e. System organ class/ Preferred terms / Reported terms
- Duration (start and end dates)
- Seriousness criteria
- Toxicity grade
- Severity
- Causality
- Outcome

The following parameters will be summarised for the subject's adverse events as mentioned in eCRF

- Number of participants with at least one TEAEs
- Number of participants with at least one drug related TEAEs
- Number of participants with at least one serious TEAEs
- Number of participants with at least one drug related serious TEAEs
- TEAE by Severity
- TEAEs leading to Death
- Drug-related TEAEs leading to Death
- TEAEs leading to early withdrawn of study
- Injection site Adverse events

Derivations:

- If adverse event start date ≥ Study drug administration start date, then we will consider it as TEAE.
- If adverse event start date ≥ Study drug administration start date and adverse event related to study treatment = "YES", then we will consider it as drug related TEAEs.

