- If adverse event start date ≥ Study drug administration start date and adverse event serious = "YES", then we will consider it as serious TEAEs.
- If adverse event start date ≥ Study drug administration start date and adverse event serious = "YES" and adverse event related to study treatment = "YES", then we will consider it as drug related serious TEAEs.

Page 42 of 85

- If adverse event start date ≥ Study drug administration start date and subject's primary reason for discontinuation = "DEATH", then we will consider it as TEAEs leading to Death.
- If adverse event start date ≥ Study drug administration start date and subject's primary reason for discontinuation = "DEATH" and adverse event related to study treatment = "YES", then we will consider it as Drug-related TEAEs leading to Death.
- If adverse event start date ≥ Study drug administration start date and subject's primary reason for discontinuation = "ADVERSE EVENT", then we will consider it as TEAEs leading to early withdrawn of study.
- If the question "were the injection site reaction(s) recorded in AE form" is answered as "YES" in eCRF "Injection Site Reaction" form, then we will consider it as Injection site Adverse events

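### The SAP flags adverse events as leading to death or to withdrawal from the subject's discontinuation reason, not from the event itself, so SOC/PT rows and the drug-related death count can be misattributed

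*SAP*

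**What the plan says.** SAP 16.1 (adverse events, derivations) defines three flags. Each requires the AE to start on or after the start of study drug, plus the following:

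- **Death.** If the subject's primary reason for discontinuation is DEATH, "then we will consider it as TEAEs leading to Death".
- **Drug-related death.** If, in addition, that AE is marked as related to study treatment, "then we will consider it as Drug-related TEAEs leading to Death".
- **Withdrawal.** If the subject's primary reason is ADVERSE EVENT, "then we will consider it as TEAEs leading to early withdrawn of study".

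The reason comes from the End of Study form. SAP 10.1 introduces it as "Subject's primary reason for discontinuation (reasons mentioned in eCRF" and offers a list of reasons, of which one is recorded as primary for each subject.

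The same section, SAP 16.1, plans to list for each AE its relationship, its outcome and "Action taken with the study treatment", and for each SAE its seriousness criteria. None of the three derivations uses the outcome, the action taken or the seriousness criteria. SAP 16.2.6 to 16.2.8 send the flags into frequency tables by SOC and PT, with listings for the two death categories, and do not restrict them further.

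**The concern.** A subject who dies or withdraws because of an AE will often have had other AEs. The rule gives all of them the same label, including events that resolved long before. The table heading makes a causal statement about each event, while the derivation establishes only that the event happened in a subject who later died or withdrew.

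The drug-related death table is the most exposed. The relatedness condition is checked on each AE, but the death condition is checked on the subject, so the related event and the fatal event need not be the same one.

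The rule can also miss events. If an AE caused death or withdrawal but another primary reason was recorded, the event does not appear.

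This is a safety study run as a condition of marketing approval, and SAEs and TEAEs are a secondary endpoint. Any fatal or withdrawal rows will be few, and each will be read closely.

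**Working it through.** The documents state no figure on this point, so there is nothing to reproduce. The check applies the SAP rules literally to an example and compares them with an event-level rule.

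**Invented example (not trial data)**

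- Subject A, reason DEATH: myocardial infarction (fatal, not related), hypoglycaemia (related, not fatal), injection site pain (related, not fatal).
- Subject B, reason ADVERSE EVENT: rash (the cause of withdrawal), nasopharyngitis, headache.

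| Flag | SAP rule: events (subjects) | Event-level rule: events (subjects) |
|---|---|---|
| Leading to death | 3 (1) | 1 (1) |
| Drug-related, leading to death | 2 (1) | 0 (0) |
| Leading to withdrawal | 3 (1) | 1 (1) |

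Three things follow.

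1. A subject with m TEAEs besides the causal one contributes 1 + m flagged events. Here m = 2, which gives 3.
2. The overall subject counts for death and for withdrawal agree under both rules (1 and 1). The error lies in the SOC/PT rows and the death listings, where two preferred terms too many appear for each subject.
3. The drug-related death count is different: 1 subject instead of 0. With the planned 250 enrolled as denominator, 1/250 = 0.4% is reported where the true figure is 0%.

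**How easily one false flag arises.** Assume that the number of other TEAEs per affected subject is Poisson with mean m. The documents give no value, so a range is shown. With k subjects whose reason is DEATH or ADVERSE EVENT, P(at least one false flag) = 1 − exp(−m·k).

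| m | k = 1 | k = 3 |
|---|---|---|
| 0.5 | 39% | 78% |
| 1 | 63% | 95% |
| 2 | 86% | 99.8% |

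For example, m = 1 and k = 3 gives 1 − exp(−3) = 0.950. These figures cover any false flag in the death or withdrawal tables. The chance of a false drug-related death is smaller, because it also needs a death judged unrelated and a related non-fatal TEAE in the same subject.

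**Missed events.** Protocol 8.2 places withdrawal for persistent hypoglycemia or a raised risk of it under investigator decision, and SAP 10.1 offers PHYSICIAN DECISION as a reason. If a withdrawal caused by hypoglycemia is recorded that way, the AE is absent from the withdrawal table.

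**The case against.** The strongest reply is that the effect is limited and the correct attribution remains visible.

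- **The tables are not bound to be wrong.** A reader might infer from the rule that they must be. The documents do not support that. An error needs a subject with reason DEATH or ADVERSE EVENT who has another TEAE, or a recorded reason that disagrees with the causal AE. No expected rate of deaths or AE withdrawals is given, and the 20% drop-out assumption covers all causes. This stands.
- **The summaries count subjects, not events.** Protocol 10.3.2.4 reports the proportion of subjects with each TEAE, and SAP section 9 uses participants as the denominator. A reader might reason that 5 AE withdrawals with 3 TEAEs each would show as 15 instead of 5 (5 × 3 = 15). That is the event count. The overall row still reads 5 subjects, and only the SOC/PT rows gain entries. This stands.
- **Only death has a drug-related version.** A reader might assume that a drug-related withdrawal table is affected too. The SAP plans none.
- **Individual data are reported alongside.** The AE and SAE listings show outcome, relationship and seriousness criteria, and protocol 9.2.1 puts the investigator's view of relationship into the SAE narrative. A false flag could be detected by comparing the two. This reduces the harm, but it leaves a summary table that contradicts its own listing.
- **How often events would be missed is unknown.** The documents do not show how often an AE withdrawal would be recorded under another reason. It is a possibility, not a forecast.

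The primary hypoglycemia endpoint does not use these flags and is unaffected.

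**Conclusion.** The derivation is wrong as written: a subject-level reason stands in for an event-level attribution, and nothing elsewhere in the SAP narrows it. The consequences depend on the data. If any subject with reason DEATH or ADVERSE EVENT has a non-causal TEAE, the SOC/PT rows for death or withdrawal, and the death listings, will contain events that did not lead to the outcome. Overall subject counts for death and withdrawal may still be correct. The drug-related death table can be wrong even in its subject count, and one such subject is enough to report a drug-related fatal TEAE that did not occur. The example and the Poisson range above rest on assumptions and show how the error arises, not how large it will be in this trial. This should be fixed before database lock. It does not threaten the primary analysis.

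**What to change.** Change SAP 16.1 as follows:

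- **TEAE leading to death:** a TEAE whose own outcome, or seriousness criterion, is fatal.
- **Drug-related TEAE leading to death:** that same AE, also marked related.
- **TEAE leading to withdrawal from study:** keep the subject-level reason ADVERSE EVENT for the subject count. In the SOC/PT rows, show only the AE identified as the cause. Take it from a link on the End of Study form if the eCRF has one. Otherwise identify and document it before database lock.
- **TEAE leading to discontinuation of treatment:** tabulate separately the AEs whose action taken was withdrawal of study drug. This should not replace the study-withdrawal table, because protocol 8.1 and 8.2 treat stopping treatment and leaving the study as different things.

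The death flags need no new data, since outcome, seriousness criteria and relationship are already planned per event. The documents do not show whether the End of Study form links to a specific AE, so the withdrawal part may need a short review of the subjects concerned. Otherwise the cost is SAP wording and a few lines of code.

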### **5.2. Number of Participants**

Assuming a 15% screen failure rate, approximately 295 subjects will be screened, so that 250 subjects can be enrolled. Assuming a drop-out rate of 20%, the target is to have a minimum of 200 subjects completing the present study.

In the India subpopulation of ELEMENT 5 study, 5 of the 46 insulin-naïve subjects experienced at least 1 hypoglycemic event (total hypoglycemia incidence with glucose levels  $\leq 54$  mg/dL [3.0 mmol/L]) during the overall study period. When considering the total ELEMENT 5 population, 146 out of 489 subjects (30%) experienced at least 1 hypoglycemic event during the overall study period. Based on these estimates, the precision with 250 and 200 subjects would be as outlined in [Table ABEX.3](#) (95% confidence interval for proportion shown based on normality assumption).

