## **9.2. Adverse Events**

Investigators are responsible for monitoring the safety of subjects who have entered this study and for alerting Lilly or its designee of any event that seems unusual, even if this event may be considered an unanticipated benefit to the subject.

The investigator is responsible for the appropriate medical care of subjects during the study.

Investigators must document their review of each laboratory safety report.

The investigator remains responsible for following, through an appropriate health care option, AEs that

- are serious or otherwise medically important
- are considered related to the investigational product or the study, or
- cause the subject to discontinue the investigational product before completing the study.

The investigator will record all relevant AE/SAE information in the eCRF. The subject should be followed until the event

- resolves
- stabilizes with appropriate diagnostic evaluation, or

- is reasonably explained.

The frequency of any additional follow-up evaluations of AEs between site and telephonic visits is left at the discretion of the investigator.

After the ICF is signed, study site personnel will record the occurrence and nature of each subject's preexisting conditions, including clinically significant signs and symptoms of the disease under treatment in the study in eCRFs. In addition, site personnel will record any change in the condition(s) and any new conditions as AEs. Investigators should record their assessment of the potential relatedness of each AE to protocol procedure and investigational product in the eCRFs.

The investigator will interpret and document whether or not an AE has a reasonable possibility of being related to study treatment, study device, or a study procedure, taking into account the disease, concomitant treatment, or pathologies.

A "reasonable possibility" means that there is a cause and effect relationship between the investigational product, study device, and/or study procedure and the AE.

The investigator answers yes or no when making this assessment.

Planned surgeries and nonsurgical interventions should not be reported as AEs unless the underlying medical condition has worsened during the course of the study.

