#### 10.3.2.4. Adverse Events Analyses

Adverse events will be listed by

- subject
- system organ class (SOC)
- Medical Dictionary for Regulatory Activities® preferred term (PT)
- severity, and
- relationship to the study disease, drug, device, or procedure for all subjects.

Adverse events (including injection site reactions and neoplasms) will be summarized as TEAEs for the FAS population. Treatment-emergent AEs are defined as events that are newly reported after the first study drug treatment or are reported to have worsened in severity after the first study drug treatment. The proportion of subjects experiencing each TEAE will be presented by PT, SOC, and treatment group. The proportion of subjects experiencing each TEAE that is assessed as possibly related to the study disease, drug, or procedures will also be summarized. Treatment-emergent AEs will be summarized by PT within SOC and by PT by decreasing frequency.

All SAEs will be listed by subject and summarized by treatment as counts and percentages. Similar analyses will be performed for discontinuations due to AEs.

All AEs analyses will be repeated for the PPS population.

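### The SAP's injection-site adverse event item rests on a form cross-reference answer instead of on adverse event records, so it miscounts where the two forms disagree

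*SAP*

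**What the plan says.** Protocol 10.3.2.4 states: "Adverse events (including injection site reactions and neoplasms) will be summarized as TEAEs for the FAS population". It attaches no condition about a second form.

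Protocol 9.2 sets the recording duty: "site personnel will record any change in the condition(s) and any new conditions as AEs".

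SAP 16.1 includes "Injection site Adverse events" in its list of adverse event parameters to be summarised. The derivation for that item, last in the section, has a single condition: the answer on the eCRF Injection Site Reaction form to "were the injection site reaction(s) recorded in AE form" must be YES.

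The general rule in the same list works differently, from the event record: "If adverse event start date ≥ Study drug administration start date, then we will consider it as TEAE".

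SAP 16.2.1 to 16.2.10 and 20.2.1 set out the adverse event outputs. None is specific to injection-site events, and none draws on the Injection Site Reaction form.

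**The concern.** The question on the dedicated form is a cross-check between two forms. The SAP uses it as the definition of the event. Whether a subject is counted in the item then depends partly on how the site completed the paperwork, and not only on whether a reaction occurred after dosing.

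The YES also identifies no event. The question covers one or more reactions together, and the rule names no AE record, preferred term, severity or onset date. The item appears in the 16.1 list, but no part of 16.2 gives it a population or a statistic, so the programmer has to choose.

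At stake is one summary line for a local harm that the protocol names, in a single-arm safety study of a self-injected product. The primary hypoglycemia endpoint is untouched.

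**Working it through.** The plan gives no figure to reproduce. The check is to follow each possible recording pattern through the SAP rules.

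**Step 1: compare the derivations.** SAP 16.1 gives seven derivations that require AE onset on or after first dose: TEAE, drug-related, serious, drug-related serious, leading to death, drug-related leading to death, and leading to early withdrawal. The injection-site rule is the eighth. It is the only one with no date test and the only one that does not start from an AE record.

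**Step 2: follow the patterns.**

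| Where the reaction is recorded | Injection-site item | General TEAE tables |
|---|---|---|
| Both forms, answer YES, onset on or after first dose | Counted | Counted |
| Dedicated form only, answer NO or blank | Not counted | Not counted |
| AE form only, dedicated form not completed | Not counted | Counted |
| Both forms, answer YES, onset before first dose | Counted | Not counted |

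The second row is the only one in which a collected reaction reaches no table. In the third row the reaction is reported by SOC and PT, by severity and by relatedness (SAP 16.2.1, 16.2.2, 16.2.5), but the item disagrees with those tables. The fourth row follows from the missing date test and would add to the item.

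**Step 3: illustrate the size.** The documents give neither a reaction rate nor a cross-recording rate, so both are assumed. The planned enrolment of 250 (Protocol 5.2: "approximately 295 subjects will be screened, so that 250 subjects can be enrolled") stands in for the FAS.

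Reported % = 100 × (affected subjects × share cross-recorded, as a whole number) / 250, with Clopper-Pearson 95% limits.

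| Assumed affected | Share cross-recorded | Item shows | 95% CI |
|---|---|---|---|
| 12 | 100% | 12/250 = 4.8% | 2.5 to 8.2 |
| 12 | 80% | 9.6, taken as 10; 10/250 = 4.0% | 1.9 to 7.2 |
| 12 | 50% | 6/250 = 2.4% | 0.9 to 5.2 |
| 12 | 0% | 0/250 = 0% | 0 to 1.5 |
| 5 | 50% | 2.5, taken as 2; 2/250 = 0.8% | 0.1 to 2.9 |
| 25 | 50% | 12.5, taken as 12; 12/250 = 4.8% | 2.5 to 8.2 |

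With full cross-recording, 5 and 25 affected subjects would be shown as 2.0% and 10.0%. The table shows how the rule behaves. It is not an estimate for this trial.

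**The case against.** The strongest reply is that the protocol's requirement is already met by another route. Protocol 9.2 has sites record new conditions as AEs. Such a record is MedDRA-coded and enters the TEAE tables by its start date, whatever the dedicated form says, and the AE listing carries its dates, severity and relationship. This stands. A reader might infer that the SAP counts an injection-site reaction anywhere only if the form says YES; the documents do not support that, because the rule governs one item.

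Second, a loss needs a departure from Protocol 9.2 that survives data cleaning. Protocol Appendix 3.2 plans computer edits, a database quality review and checks against source, and the form question itself looks like a built-in check. This also stands, and it makes the loss conditional. It does not repair the definition, since the SAP does not say what happens to a NO that remains at lock.

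Third, the eCRF is not in the documents. The form may carry an AE number, or a NO may have a meaning that cannot be seen here, and the Schedule of Activities lists no separate injection-site assessment. That is a fair limit. What can be said is that the SAP uses no such link.

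Fourth, a reader might infer that the item can only be too low. Missing cross-recording lowers it, but the absent first-dose test could raise it, so the net direction is not established.

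Fifth, a reader might infer that a YES can never be tied to severity or relatedness. Those data sit on the AE record; what is missing is the instruction to use them.

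**Conclusion.** The point holds in a limited form. SAP 16.1 defines the injection-site item by a form answer and not by an event, and 16.2 specifies no analysis for it. The consequence is confined to that item and to records on which the two forms disagree. A reaction held only on the dedicated form reaches no SAP table, and one held only on the AE form is absent from the item while still present in the TEAE tables.

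No size can be given from the documents. Under the assumed inputs, half cross-recording halves the item apart from rounding (4.8% to 2.4% for 12 of 250), and full cross-recording loses nothing. The conclusion assumes that the SAP text is the whole specification and that no unseen eCRF link is applied in programming.

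This is a minor reporting correction. It does not bear on the primary endpoint, on the TEAE and SAE tables for events recorded as the protocol requires, or on clinical management.

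**What to change.** In SAP 16.1, replace the derivation. An injection-site adverse event is any AE record whose MedDRA term is on a prespecified injection-site list and whose start date is on or after first dose, with each subject counted once.

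In SAP 16.2, add an entry for the item: FAS, n (%) overall and by severity.

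Use the cross-reference answer only to reconcile the two forms and raise queries before database lock. List any reaction that is still only on the dedicated form at lock and count it separately, using a date or severity only where that form collects one.

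The cost is revised SAP wording, one extra listing and one table row. No new procedure or visit is needed.
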